#### 4.3.12.1.2 Presentation

Duration of exposure to Investigational Products (IP)(s) in weeks and cycles are summarised by descriptive statistics and by frequency for each treatment arm. Dose intensity is summarised by descriptive statistics. Exposure to IP(s) i.e. total amount of study drug received is listed for all subjects. Exposure swimmer plot(s) are produced, with a line presented for each subject to display relevant exposure and disposition details.

Dosing deviations for IP(s) are summarised with reasons for deviations for the following categories: delays, reductions, and interruptions. Dosing delays are derived based on the scheduled dosing dates using the previous dose given as reference. The number and percentage of subjects with dosing delays and total dose delays per subject are summarised.

#### 4.3.12.2 Adverse Events

# 4.3.12.2.1 Definitions and Derivations

The Medical Dictionary for Regulatory Activities (MedDRA) (version 25 or higher) is used to code the AEs. AEs are graded according to the National Cancer Institute Common Terminology Criteria for AEs (CTCAE) (version 5.0).

Treatment emergent adverse events (TEAEs) are all AEs which onset or worsen in severity following the first administration of IP within the duration of the treatment period, up to

and including 30 days after the last dose of study treatment for ceralasertib monotherapy or 90 days after last dose of study treatment for ceralasertib and durvalumab combination, and prior to the start of any subsequent anti-cancer therapy,. Worsening in severity is determined by comparison with the pre-treatment CTCAE grade of the AE recorded closest to the start of dosing.

AEs with a missing start time or where time is not collected, which occur on the same day as first IP administration, are reported as treatment emergent.

For rules on missing or partial dates, see Section 3.4.6.

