## **3.2** General Considerations

The below-mentioned general principles will be followed throughout the study:

- Summary tables are produced by treatment group. Total columns are produced for non-efficacy tables.
- Descriptive statistics will be used for all variables, as appropriate.
  - Continuous variables will be summarised by the number of observations, mean, standard deviation, median, upper, and lower quartiles where indicated, minimum and maximum. For log-transformed data (ie, pharmacokinetic [PK] concentration data) it is more appropriate to present geometric mean, coefficient of variation (CV), median, minimum, and maximum.
  - If data are available for less than 3 subjects, no summary statistics other than minimum, maximum and number of observations are presented.
  - Categorical variables will be summarised by frequency counts and percentages for each category. Unless otherwise stated, percentages will be calculated based on the analysis set population total, by treatment group and by timepoint as appropriate.
- For continuous data, the mean, standard deviation and median are rounded to one additional decimal place compared to the original data. Minimum and maximum are displayed with the same accuracy as the original data.
- Time-to-event variables will be presented using the Kaplan-Meier (KM) methodology, including median time calculated from the KM curves.
- For categorical data, percentages are rounded to one decimal place with the exception of 100% which is presented as a whole number.
- SAS® version 9.4 (or higher) and/or other validated software (as appropriate) will be used for the analyses. In case R is used, the R build version and the version of each used R package will be documented.

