## 3.2.4 On-treatment

For the purposes of summarizing safety data assessed at visits, in addition to baseline data, only on-treatment data are included in the summary tables. On-treatment data is defined as data on/after the first dose of study treatment and with assessment date up to and including the date of last study treatment + 30 days (safety follow-up) for ceralasertib monotherapy or the date of last study treatment + 90 days (safety follow-up) for ceralasertib and durvalumab combination, and prior to the start of any subsequent anti-cancer therapy.

The on-treatment period therefore comprises of the treatment period (first administration of any study treatment to and including last day of administration of any study treatment) and the safety follow-up period (30 days after last administration for ceralasertib monotherapy or 90 days after last administration for ceralasertib and durvalumab combination), and prior to the start of any subsequent anti-cancer therapy.

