#### 4.3.12.2.2 Presentation

All TEAEs will summarised and listed. AEs which are not treatment emergent will be listed for the Safety analysis set and will be listed individually by subject and treatment arm.

TEAEs will be counted once for each subject for calculating percentages of subjects experiencing TEAE. In addition, if the same TEAE occurs multiple times within a particular subject, the highest severity and level of relationship observed will be reported. For tables by MedDRA system organ class (SOC) and MedDRA preferred term (PT), subjects with multiple TEAEs will be counted once for each SOC/PT.

An overall summary table of the number of subjects experiencing each category of adverse event will be produced. The number of subjects experiencing treatment emergent adverse events by MedDRA SOC and PT will be summarised and incidence rates will be provided. Severity and relationship to IP will be summarised. Further splits by CTCAE grade, causal relationship to IP and adverse events with Grade 3-4 will be also summarised.

Separate tables will present adverse events leading to discontinuation, serious adverse events, IP-related adverse events, and other significant adverse events.

Details of any deaths will be summarised and listed for all subjects. AEs leading to death will also summarised.

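### TEAE, SAE and AESI percentages are set side by side and pooled, although events count for up to 90 days after last dose in the combination arm and up to 30 in the monotherapy arm

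*SAP*

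**What the plan says.** All references are to the main-study SAP.

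- **Counting window, AEs (4.3.12.2.1).** Treatment-emergent events run to "30 days after the last dose of study treatment for ceralasertib monotherapy or 90 days after last dose of study treatment" for the combination. The same sentence adds a limit for both arms: "and prior to the start of any subsequent anti-cancer therapy".
- **Counting window, visit-based safety data (3.2.4).** The same periods apply: "30 days after last administration for ceralasertib monotherapy or 90 days after last administration for ceralasertib and durvalumab combination".
- **Measure (4.3.12.2.2).** "TEAEs will be counted once for each subject for calculating percentages of subjects experiencing TEAE". The SAE paragraph follows the TEAE method, and the AESI paragraph reports number and percentage of subjects. Events that are not treatment emergent are only listed.
- **Denominator (3.2).** Unless stated otherwise, percentages use the analysis set total for the arm.
- **Layout (3.2).** "Summary tables are produced by treatment group. Total columns are produced for non-efficacy tables".
- **A possible time adjustment (4.3.12.2.2).** The number of subjects with "treatment emergent adverse events by MedDRA SOC and PT will be summarised and incidence rates will be provided". No denominator or formula is given for these rates.

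**The concern.** A percentage of subjects with at least one event depends on how long each subject is observed. Here the observation time after last dose differs by arm through the definition itself, and the denominator ignores it. Take two subjects, one per arm, with the same event on Day 45 after last dose and no subsequent therapy. The combination subject is a case in the TEAE tables. The monotherapy subject appears in a listing at most.

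The trial randomises to ceralasertib with or without durvalumab, so the side-by-side AE, SAE and AESI columns are a natural place to look for the toxicity that durvalumab adds. Part of any difference seen there would come from the counting rule. The Total column combines two definitions of a case in one percentage.

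**Working it through.** The SAP states no AE rate or safety precision, so there is no figure of its own to reproduce. The check asks what the tables would show if the arms did not differ at all.

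**Inputs from the SAP:** windows w = 30 and 90 days (4.3.12.2.1); about 100 and 50 subjects (3.2.2); counting stops at subsequent therapy.

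**Assumptions, not in the SAP:** a constant event hazard λ, equal in both arms and unchanged after last dose; equal time on treatment T in both arms; exponential time from last dose to subsequent therapy with rate μ.

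**Formulas**

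- Without subsequent therapy: risk = 1 − exp(−λ(T + w)).
- With subsequent therapy: risk = 1 − exp(−λT) × [μ + λ exp(−(λ + μ)w)] / (λ + μ), where μ = ln 2 / median.

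**Central case:** T = 112 days and a 5% event risk per 30 days, so λ = −ln(0.95)/30 = 0.00171 per day.

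- Combination: 1 − exp(−0.00171 × 202) = 29.2%.
- Monotherapy: 1 − exp(−0.00171 × 142) = 21.6%.
- Difference 7.6 points; ratio of observation time 202/142 = 1.42.
- Total column: (100 × 29.2 + 50 × 21.6)/150 = 26.7%, which corresponds to neither window.

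| Median time to subsequent therapy | Combination | Monotherapy | Gap (points) |
|---|---|---|---|
| None | 29.2% | 21.6% | 7.6 |
| 60 days | 24.8% | 20.9% | 3.9 |
| 30 days | 22.5% | 20.4% | 2.1 |
| 14 days | 20.2% | 19.6% | 0.6 |

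**Varying the other assumptions, no subsequent therapy**

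- T = 56 days, 5% per 30 days: 22.1% vs 13.7%.
- T = 168 days, 5% per 30 days: 35.7% vs 28.7%.
- T = 112 days, 2% per 30 days: 12.7% vs 9.1%.
- T = 112 days, 10% per 30 days: 50.8% vs 39.3%.

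**Extreme case:** last dose in cycle 2, no subsequent therapy. On the planned schedule, monotherapy ends on Day 35 and the combination on Day 36, so countable time is 35 + 30 = 65 and 36 + 90 = 126 days (ratio 1.94). At 0.002 per day this gives 12.2% vs 22.3%.

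**After the fix:** with a 30-day window in both arms, the central case without subsequent therapy gives 21.6% in each. With first events per person-time on the existing windows, the simulated ratio of the arms is 1.00.

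**The case against.** **The windows are appropriate.** A longer safety follow-up for the regimen containing durvalumab is not an error. This stands; the point concerns only the comparison and pooling of raw percentages across the two windows.

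**Subsequent therapy cuts the window.** A reader might infer that every combination subject is observed for 60 days longer. The SAP does not support that. Counting stops at subsequent therapy, so 60 days is a maximum. Subjects who start new therapy or die soon after last dose, or who are still on treatment at data cut-off, gain little or nothing. This shrinks the gap but does not reverse it.

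**Laboratory worst grades.** A reader might extend the point to these. The text does not allow it as it stands: section 4.3.12.3.2 presents laboratory abnormalities and worst grades up to the last assessment on study, whereas sections 3.2.4 and 3.2.5 limit summaries to on-treatment data. Which period applies is unclear, so laboratory results are left out here.

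**Incidence rates are promised.** They could mean time-adjusted rates, but no denominator is given and section 3.2 defaults to subject totals. The mention does not settle the matter; defining it would.

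**Safety is descriptive.** No between-arm AE test, risk difference or ratio is planned, exposure is reported by arm, and later monotherapy events would be listed if collected. That limits the weight of the point. Percentages in adjacent columns of a randomised trial still invite comparison, and the Total column is a pooled estimate whatever the reader intends.

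**The hazard may fall after last dose.** Events confined to dosing days are unaffected, so the constant-hazard figures overstate the gap for such events.

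**Conclusion.** The point holds for the TEAE, SAE and AESI percentages. If event rates and time on treatment are equal and events continue after last dose, the combination arm has the higher expected percentage through the window alone. The direction is the same in every scenario examined.

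The SAP does not fix the size. At 5% per 30 days and 112 days on treatment, the gap runs from under 1 point (subsequent therapy at a median of 14 days), through about 4 points (median 60 days), to about 8 points (none). It is larger for early stoppers without subsequent therapy. The near-doubling of observation time in the two-cycle case is correct arithmetic at the edge of the range. A reader should not infer that the tables will make the combination look twice as toxic. Hazard, treatment duration and time to subsequent therapy are all assumed.

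This is a worthwhile and cheap improvement to a descriptive safety section; the follow-up periods themselves are not at fault.

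**What to change.** Keep the 30/90-day tables as each regimen's own safety profile, and footnote the window lengths on them, including what the Total column combines.

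In section 4.3.12.2.2, add one of the following:

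- a common-window version (first dose to last dose plus 30 days, before subsequent anti-cancer therapy) of the side-by-side and Total overview, SOC/PT, Grade 3 or higher, SAE and AESI tables; or
- a definition of incidence rates as subjects with a first event divided by person-time at risk, with each subject's time running to the first event or the end of that subject's countable period.

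The cost is a few repeated tables, with no change to follow-up or data collection. The common window leaves out late events in the combination arm; these remain in the 90-day tables.

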#### SAEs

A serious adverse event (SAE) is any AE that:

- Results in death
- Is immediately life-threatening
- Requires inpatient hospitalisation or prolongation of existing hospitalisation
- Results in persistent or significant disability/incapacity.
- Is a congenital anomaly/birth defect in offspring of the subject
- Is an important medical event that may jeopardize the subject.

#### **Adverse Events of Special Interest (AESI)**

Adverse events of special interests are events of scientific and medical interest specific to the further understanding of ceralasertib and durvalumab safety profile and require close monitoring and rapid communication by the investigators to AstraZeneca. An AESI can be serious or non-serious. All AESIs will be recorded in the eCRF. Additionally, AESI will be identified programmatically using a definition file maintained by Astra Zeneca.

Adverse events of special interests for durvalumab include but are not limited to events with a potential inflammatory or immune-mediated mechanism and which may require more frequent monitoring and/or interventions such as steroids, immunosuppressants and/or hormone replacement therapy. An immune-mediated AE is defined as an AESI that is associated with drug exposure and is consistent with an immune-mediated mechanism of action and where there is no clear alternate aetiology.

If the investigator has any questions in regards to an event being an immune-mediated AE, the investigator should promptly contact the AstraZeneca study physician or clinical lead.

Adverse events of special interests/ immune-mediated AE observed with anti-PD-L/PD-1 agents such as durvalumab include pneumonitis, hepatitis, diarrhoea/colitis, intestinal perforation, endocrinopathies (hypo- and hyperthyroidism, adrenal insufficiency,

hypophysitis/hypopituitarism and Type 1 diabetes mellitus), nephritis, rash/dermatitis, myocarditis, myositis/polymyositis, pancreatitis and rare/less frequent events (including, but not limited to haematological events, neuromuscular toxicities [such as myasthenia gravis and Guillain-Barré syndrome], non-infectious encephalitis, non-infectious meningitis, pericarditis, rheumatological events, sarcoidosis, skin events, uveitis [and other events involving the eye] and vasculitis).

In addition, infusion-related reactions and hypersensitivity/anaphylactic reactions with a different underlying pharmacological aetiology are also considered AESIs.

More detailed guidelines for their evaluation and treatment are described in detail in the Dose Modification and Toxicity Management Guidelines (version 28-Oct-2021). These guidelines have been prepared by the sponsor to assist the investigator in the exercise of his/her clinical judgement in treating these types of toxicities. These guidelines apply to AEs considered causally related to the study treatment/study regimen by the reporting investigator.

There are no currently identified AESI for Ceralasertib but if any are identified, these will be reported in similar/appropriate outputs to the durvalumab AESI.

#### Other significant adverse events (OAE)

During the evaluation of the AE data as part of the monthly offline listing review process, an AstraZeneca medically qualified expert reviews the list of AEs that were not reported as SAEs and AEs leading to discontinuation of study treatment after Parexel's review took place. Based on the expert's judgement, adverse events of particular clinical importance may, after consultation with the Global Safety Physician, be considered OAEs and reported as such in the CSR. A similar review of laboratory values, vital signs, ECGs and other safety assessments are performed for identification of other significant adverse events. This review takes place prior to database lock, and any AEs identified are fully documented in meeting minutes. Further review following database lock may result in ad-hoc OAEs being identified, in this case, the OAEs and resulting summaries are fully documented in the CSR.

Examples of these are marked haematological and other laboratory abnormalities, and certain events that lead to intervention (other than those already classified as serious), dose reduction or significant additional treatment.

#### 4.3.12.2.2 Presentation

All TEAEs will summarised and listed. AEs which are not treatment emergent will be listed for the Safety analysis set and will be listed individually by subject and treatment arm.

TEAEs will be counted once for each subject for calculating percentages of subjects experiencing TEAE. In addition, if the same TEAE occurs multiple times within a particular subject, the highest severity and level of relationship observed will be reported. For tables by MedDRA system organ class (SOC) and MedDRA preferred term (PT), subjects with multiple TEAEs will be counted once for each SOC/PT.

An overall summary table of the number of subjects experiencing each category of adverse event will be produced. The number of subjects experiencing treatment emergent adverse events by MedDRA SOC and PT will be summarised and incidence rates will be provided. Severity and relationship to IP will be summarised. Further splits by CTCAE grade, causal relationship to IP and adverse events with Grade 3-4 will be also summarised.

Separate tables will present adverse events leading to discontinuation, serious adverse events, IP-related adverse events, and other significant adverse events.

Details of any deaths will be summarised and listed for all subjects. AEs leading to death will also summarised.

#### SAEs

SAEs are summarised as described above for the TEAEs.

#### AEs of special interest

Grouped summary tables of certain MedDRA preferred terms are produced and may also show the individual preferred terms which constitute each AESI grouping. These groupings may be defined using MedDRA terms, SMQs (standardized MedDRA queries) and PTs (preferred terms). Groupings are provided by the coding team prior to DBL, and a listing of the preferred terms in each grouping is provided. Summaries of the above-mentioned grouped AE categories include number and percentage (%) of subjects who have:

- At least one AESI presented by event outcome
- At least one AESI causally related to IP
- At least one AESI leading to discontinuation of study treatment.

A summary of total duration (days) of AESI are provided for events which have an end date and this may be supported by summaries of ongoing AESIs at death and, separately, at data cut-off.

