## 3.2.8 Missing Dates

Generally, the imputation of dates is used to decide if an observation is treatment emergent for adverse events (AEs) or concomitant medications. Flags are retained in the database indicating where any programmatic imputation has been applied, and in such cases, any imputed dates should not be used to calculate durations, where the results would be less accurate.

The following are the guidelines used when partial dates are detected in the study:

- For missing diagnostic dates (e.g. disease diagnosis), if day and/or month are missing use 01 and/or Jan. If year is missing, put the complete date to missing.
- For missing AE and concomitant medication start dates, the following is applied:
  - a. Missing day— impute the 1st of the month unless month is the same as month of the first dose of study drug then impute first dose date.
  - b. Missing day and month-- impute 1st January unless year is the same as first dose date then impute first dose date.
  - c. Completely missing— impute first dose date unless the end date suggests it could have started prior to this in which case impute the 1st January of the same year as the end date.
  - d. Imputed start date should be no later than the end date.
- For missing AE and concomitant medication end dates, the following is applied:
  - a. Missing day— impute the last day of the month unless month is the same as month of study discontinuation, then impute as study discontinuation date.
  - b. Missing day and month-- impute 31st December unless year is the same as year of study discontinuation then impute study discontinuation date.

- c. Completely Missing If an AE/medication has a completely missing end date then it is treated as ongoing, unless this is for a prior anti-cancer medication then impute the date of informed consent.
- If a subject are known to have died where only a partial death date is available then the date of death is imputed as the latest of the last date known to be alive +1 from the database and the death date using the available information provided:
  - a. For Missing day only using the  $1^{st}$  of the month.
  - b. For Missing day and Month using the 1st of January.

For patients with a treatment start date for ceralasertib, the following rules are applied for missing treatment end dates for ceralasertib:

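### The only committed AESI duration summary covers events that have ended, so it runs short if read as the duration of all AESIs; the ongoing-event counts that would show this are optional

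*SAP*

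**What the plan says.** The AESI presentation text is the same in both SAPs (main 4.3.12.2.2, sub-study 4.3.14.2.2). It commits to a duration summary limited to ended events: "A summary of total duration (days) of AESI are provided for events which have an end date". The same sentence continues that "this may be supported by summaries of ongoing AESIs at death and, separately, at data cut-off". That clause is permissive, not a commitment.

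The same section also lists, without qualification, counts and percentages of subjects with "At least one AESI presented by event outcome".

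Two rules in section 3.2.8 decide which events have a usable end date. "If an AE/medication has a completely missing end date then it is treated as ongoing", so such an event falls outside the duration summary. For partial dates, "any imputed dates should not be used to calculate durations, where the results would be less accurate".

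The AESI definition (main 4.3.12.2.1, sub-study 4.3.14.2.1) includes endocrinopathies such as hypothyroidism, adrenal insufficiency, hypophysitis and type 1 diabetes, and refers to "interventions such as steroids, immunosuppressants and/or hormone replacement therapy".

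Neither SAP specifies a Kaplan-Meier, cumulative-incidence or other censored analysis of AESI duration.

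**The concern.** Duration is right-censored for any event still open when observation stops. Keeping only events with an end date selects on the quantity being measured: short events have time to end and long ones do not. The result then depends on how long subjects are observed after onset as well as on how long events last. If follow-up after onset is short, as in subjects who die early, the figure shrinks although the toxicity is the same. Two arms with different follow-up after onset could differ for that reason alone.

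The point matters more here because the AESI list includes endocrine events for which hormone replacement may be needed. That such events often stay open is a reasonable inference; the SAP does not say it. At stake is how the persistence of durvalumab immune-mediated toxicity is described. No efficacy conclusion depends on it.

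**Working it through.** The plan gives no AESI duration, count or share unresolved, so there is no figure to reproduce. Direction can be shown by reasoning. Size can only be illustrated, and **every numerical input below is an assumption**.

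**Set-up.** Time to resolution is exponential with median m, so λ = ln 2 / m. A share π never resolves. Time from onset to end of observation is uniform on 0 to F days. An event enters the planned table only if it resolves within that time.

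**Formulas.**
- Share with an end date = (1 − π) × [1 − (1 − e^(−λF)) / (λF)].
- Density of the durations that enter the table is proportional to λe^(−λt)(1 − t/F). π cancels, so the table does not respond to the share of permanent events.
- Median over all events solves π + (1 − π)e^(−λt) = 0.5, giving t = −ln[(0.5 − π)/(1 − π)] / λ.

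**One case by hand** (m = 90, π = 0.2, F = 365). λ = 0.693/90 = 0.00770 and λF = 2.81. Share ended = 0.8 × (1 − 0.940/2.81) = 0.8 × 0.666 = 0.53, so 47% are excluded. All-event median = 0.981/0.00770 = 127 days. The ended-only median from simulation is 58 days.

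**Simulation**, 400,000 events per scenario and 18 scenarios (m = 30, 90, 180; π = 0, 0.2, 0.4; F = 180, 365). Selected results, with ratios taken before rounding:

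| m (days) | π | F (days) | Excluded | Ended-only median | All-event median | Ratio |
|---|---|---|---|---|---|---|
| 30 | 0 | 365 | 12% | 26 | 30 | 0.88 |
| 30 | 0 | 180 | 24% | 22 | 30 | 0.75 |
| 90 | 0 | 365 | 33% | 58 | 90 | 0.64 |
| 90 | 0.2 | 365 | 47% | 58 | 127 | 0.45 |
| 90 | 0.4 | 365 | 60% | 58 | 233 | 0.25 |
| 90 | 0.2 | 180 | 63% | 38 | 127 | 0.30 |
| 180 | 0.4 | 365 | 72% | 77 | 465 | 0.17 |
| 180 | 0.4 | 180 | 83% | 45 | 465 | 0.10 |

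The ended-only median was below the all-event median in all 18 scenarios (ratio 0.10 to 0.88). In the 90-day, 365-day rows it stays at 58 days while the permanent share rises from 0 to 40%. With π = 0.2 it moves from 58 to 38 days when only the window shortens. In the last two rows the all-event median lies beyond the window, so a censored analysis would report it as not reached.

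**Why the remedy must treat death separately.** Death precludes resolution. Assume median resolution 60 days and median survival after onset 180 days, both exponential. If deaths are censored, 1 − Kaplan-Meier at day 180 is 1 − 0.5^(180/60) = 87.5% resolved. The proportion actually resolved before death is [(1/60)/(1/60 + 1/180)] × (1 − 0.5^(3+1)) = 0.75 × 0.9375 = 70%. Censoring at death would overstate resolution.

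**The case against.** The strongest reply is that the table states its own scope. It is declared to cover events with an end date and is correct for that scope, and no test, decision rule or stopping criterion uses it. This stands: it is not a wrong derivation, and the figure is too short only as a description of all AESIs.

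A reader might infer that lasting immune-mediated events disappear from the safety report, or that reversibility will be overstated. The document does not support either. The counts by event outcome are committed, and all treatment-emergent events are to be listed, so unresolved AESIs leave the duration figure but not the reporting. The outcome counts are, however, per subject, carry no time information, and do not show how many events the duration table left out.

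A reader might also see a breach of the general principle in section 3.2 that "Time-to-event variables will be presented using the Kaplan-Meier (KM) methodology, including median time calculated from the KM curves". The SAP nowhere designates AESI duration as a time-to-event variable, so this is not a contradiction. Treating a completely missing end date as ongoing is no error either; it avoids inventing a resolution date.

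Finally, the sponsor foresaw ongoing events. That is true, but the provision is optional, and counts alone do not tell a reader how long events last.

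**Conclusion.** The point holds in a limited form. In both SAPs the only committed AESI duration statistic describes resolved events, and read as the duration of all AESIs it is biased short. The direction follows from the selection and does not need the simulation. The size is unknown: the 0.10 to 0.88 range rests on exponential resolution, uniform follow-up after onset and chosen permanent fractions, none of which the plan supplies. It shows that the gap could be slight (26 against 30 days) or large, and it is not a forecast for this trial. Unresolved events remain visible in the outcome counts. This is a descriptive safety output and the change is a cheap improvement.

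**What to change.** Make these changes in the AESI presentation text of both SAPs:

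1. Change the permissive wording to a commitment, so that the number and percentage of AESIs ongoing at death and, separately, at DCO are always shown beside the duration table.
2. Title the duration table as resolved events only.
3. Add a time-to-resolution summary per AESI group: cumulative incidence of resolution at fixed times, with the median where estimable. Censor ongoing events at the earlier of last contact and DCO, and treat death as a competing event.
4. State a rule for repeat events within a subject, for example the first event per group.

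The cost is SAP wording and one extra descriptive table, using data already collected. In small AESI groups the median may not be estimable, and the table should then say so.
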